2.1 Objectives

2.1.1 Primary Objective

Verify whether non-sedated 3D volumetric structural magnetic resonance imaging (MRI) obtained ≥ 28 days and ≤ 4 months old can reliably discriminate between brachial plexus birth palsy (BPBP) injury patients who require surgical reconstruction versus those who will recover spontaneously.

2.1.1.1 Hypothesis:

The SRS will effectively be able to discriminate between infants who require surgical reconstruction versus those who will recover spontaneously.

2.1.2 Secondary Objective 1:

Assess whether MRI findings for pre-operative planning in infants with BPBP, specifically the level(s) and extent of injury of each nerve root and the location of root injury (pre- vs. post-ganglionic), correlate with intraoperative findings identified during brachial plexus reconstructive microsurgery.

2.1.2.1 Hypothesis:

MRI findings for pre-operative infants will exhibit characteristics similar to those found intraoperatively.

2.1.3 Secondary Objective 2:

Two standard BPBP clinical measures – the Active Movement Scale (AMS) and Toronto scores will be used to confirm clinical outcomes of our decision-making both for and against surgery.

2.1.3.1 Hypothesis:

AMS and Toronto scores will improve to functional levels at final follow-up for those subjects who were determined not to need surgery. AMS and Toronto scores will improve following surgical intervention for those subjects who undergo surgery.

3.0 Subject Selection:

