4.2.3 Standardization of indications for surgery

Surgeons will adhere to standard indications for microsurgery in infants with BPBP. These are: 1) flail arm and Horner's syndrome 2) Toronto score less than 3.5, 3) failure to recover antigravity elbow flexion and/or antigravity shoulder abduction (AMS score for elbow flexion and/or abduction less than 5), 4) failure to bring the hand to the mouth (cookie test), or other clinical indication of lack of appropriate nerve recovery.

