4.3 Study Procedures

4.3.1 Study Visits

At the baseline visit, we will collect patient demographics, prenatal and perinatal history, as well as information on any concomitant birth injuries. A standardized physical examination will be conducted at the enrollment visit and all subsequent study visits, consisting of the Toronto Score and AMS score. The Narakas score and the MRI will take place at or around the time of enrollment into the study. At the time of the MRI scan, the neuroradiologist will document the status of each nerve root as normal, post-ganglionic rupture, or pre-ganglionic avulsion, in addition to calculating the numerical SRS. For those infants who undergo microsurgery, we will document the indications for surgery, operative findings at each nerve root, and procedure performed at each nerve root.

[figure not shown]

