8.2 Secondary Study Endpoints

The secondary outcome will be the surgeon's intraoperative findings during brachial plexus reconstructive microsurgery. Specifically, agreement between MRI and intraoperative findings, with respect to the level(s) and extent of injury of each nerve root and the location of root injury (pre- vs. post-ganglionic) will be determined.

AMS and Toronto scores will be evaluated at 12, 18 and 30 months of age, which will correlate roughly with 6, 12, and 24 months post-operatively for those infants who undergo surgery.

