8.4 Statistical Methods

The primary analysis for this will be assessing the discriminant ability of the SRS system to distinguish patients who do versus do not go on to surgery, by estimating the area under the receiver operating characteristic (ROC) curve with a 95% confidence interval. In addition, an optimal cutoff value for the SRS will be identified using Youden's Index which maximizes the sum of sensitivity and specificity. Sensitivity and specificity will be estimated to help quantify the utility of the SRS system to discern between surgical patient groups. The area under the ROC curve (AUC) for the SRS system may be compared to the AUC for the AMS, currently part of clinical surgical decision making, to assess whether the MRI score offers a comparable, earlier detection method for the need for surgical intervention. Secondary analysis will include comparing MRI nerve root findings at each nerve root level (C5, C6, C7, C8, and T1) with intraoperative root findings in surgical patients. Weighted kappa coefficients along with 95% confidence intervals will be estimated to assess the concordance in detecting intact, ruptured, or avulsed roots between MRI and intraoperative inspection. In addition, inter- and intra-rater reliability of the SRS will be assessed by estimating Krippendorff's alpha along with a 95% confidence interval. The AMS and Toronto evaluations at 18 and 30 months of age in the non-operative group will be used to confirm that these patients do achieve spontaneous recovery, and will be compared with the scores for the surgery group at the same time points.

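### The hypothesis that AMS and Toronto scores improve after surgery has no matching analysis; the planned same-age comparison with unoperated infants cannot confirm or refute it

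*Combined protocol and SAP*

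**What the plan says.** Secondary Objective 2 uses AMS and Toronto scores to check the decisions made both for and against surgery. Section 2.1.3.1 splits this into two hypotheses. For unoperated infants: "AMS and Toronto scores will improve to functional levels at final follow-up for those subjects who were determined not to need surgery". For operated infants: "AMS and Toronto scores will improve following surgical intervention for those subjects who undergo surgery".

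Section 8.2 sets the ages but no method: "AMS and Toronto scores will be evaluated at 12, 18 and 30 months of age". It equates these ages, approximately, to half a year, one year and two years after an operation.

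Section 8.4 gives the analysis. "The AMS and Toronto evaluations at 18 and 30 months of age in the non-operative group will be used to confirm" spontaneous recovery, and these scores "will be compared with the scores for the surgery group at the same time points". It names no pre-operative baseline, change score, covariate, model or test.

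Sections 4.2.3 and 4.3.3 list the indications for surgery. They include "Toronto score less than 3.5" and an AMS score below 5 for elbow flexion and/or abduction. Section 4.3.1 provides the data that a before–after analysis would need: "A standardized physical examination will be conducted at the enrollment visit and all subsequent study visits", made up of the Toronto and AMS scores.

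**The concern.** The hypothesis for operated infants is about each infant's own course: the score after surgery against the score before it. The analysis in section 8.4 compares two groups of infants at one age. These are different quantities, and the second does not determine the first.

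The two groups are also separated partly on the measures later compared, since a low Toronto or AMS score is itself a reason to operate. Operated infants therefore start lower, and a lower score at 18 or 30 months is to be expected even if every one of them improved.

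At stake is the half of Secondary Objective 2 that concerns decisions for surgery. If section 8.4 is followed exactly, the trial will have no planned result that bears on it, and the one contrast it does report could make infants who improved look like poor outcomes.

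**Working it through.** **Plan's own figure.** There is none to reproduce on this point. The sample size in section 8.3 (70 evaluable infants, 30% operated, so 0.30 × 70 = 21) rests on the primary AUC aim alone. No SD, correlation or target change is given for AMS or Toronto. Everything below is in SD units and rests on stated assumptions.

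**Step 1: why the contrast does not identify improvement.** For mean scores,

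follow-up gap (operated − unoperated) = pre-operative gap + change in operated − change in unoperated.

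Assume the lowest 30% on a normal baseline score are operated. The mean of the lowest 30% is -0.3477/0.30 = -1.159 and of the rest +0.3477/0.70 = +0.497. The pre-operative gap is -1.159 − 0.497 = -1.656 SD. Assume also that unoperated infants improve by 1 SD.

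| True change in operated infants | Follow-up gap |
|---|---|
| 0 SD | -1.656 + 0 − 1 = -2.66 |
| +1 SD | -1.656 + 1 − 1 = -1.66 |
| +2 SD | -1.656 + 2 − 1 = -0.66 |
| +3 SD | -1.656 + 3 − 1 = +0.34 |

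A simulation of this set-up agrees to within 0.01 SD. Operated infants who improved by 1 or 2 SD still score below the unoperated group. Without the pre-operative scores, the sign of the contrast does not show whether operated infants improved.

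**Step 2: the gap expected when surgery does nothing.** With baseline–follow-up correlation ρ, the gap is ρ × (-1.656):

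- ρ = 0.4: -0.66 SD
- ρ = 0.6: -0.99 SD
- ρ = 0.8: -1.32 SD

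**Step 3: how often the contrast points the wrong way.** Simulated trials had 70 infants, 21 of them operated, with a true benefit of 0.5 SD against no surgery. The table shows the share of trials in which the unadjusted difference is below zero.

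| ρ | Strict lowest-30% selection | Selection with 1 SD of noise |
|---|---|---|
| 0.4 | about 0.73 | about 0.44 |
| 0.6 | about 0.98 | about 0.78 |
| 0.8 | above 0.99 | about 0.97 |

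The noisy column matters because section 4.2.3 also lists flail arm with Horner's syndrome, the cookie test and other clinical signs, so selection is not on one score alone.

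**Step 4: what a within-infant analysis could deliver.** For a paired t-test (two-sided 5%, 80% power), the detectable mean change is 0.64 SD of the change score with 21 operated infants, 0.68 with 19, 0.72 with 17 and 0.78 with 15. The range 15–21 is an assumption about loss to follow-up. The 95% CI half-width with 21 is 2.086/√21 = 0.46 SD.

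**The case against.** The plan never presents the between-group comparison as a treatment effect. The sentence in section 8.4 is mainly about confirming recovery in unoperated infants, and that half of the objective does have an analysis. A descriptive contrast between groups expected to differ is legitimate. This stands, and it limits the point. A reader might infer that the plan sets out to estimate the effect of surgery from a confounded comparison, but the documents do not say so.

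Two other readings also go too far. A reader might conclude that no pre-operative score enters any analysis. Section 8.4 includes an optional comparison of the SRS AUC with an AMS AUC, in which AMS is a predictor of surgery; that analysis does not address improvement, but it exists. A reader might also call the planned comparison unadjusted. The text names no adjustment, which is not the same as ruling one out.

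The illustration has limits too. The proportions in Step 3 depend heavily on the assumed correlation and selection noise, and no single value should be quoted alone. They concern a benefit against no surgery, whereas the hypothesis concerns change within infants; Step 1 is closer to that.

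Finally, this is a secondary objective. The primary AUC analysis and the sample size are untouched, and section 8.2 does follow operated infants by approximate time since surgery. What remains is that the stated hypothesis for operated infants has no analysis that could support or contradict it.

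**Conclusion.** The point holds in this form: section 2.1.3.1 states a before–after hypothesis for operated infants, and section 8.4 specifies no before–after analysis. The one post-operative outcome analysis it gives carries a severity gap, because low AMS and Toronto scores are among the reasons to operate.

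The mismatch and the expected direction of the gap follow from the documents. The size does not. A gap of -0.66 to -1.32 SD under no surgical effect, and a wrong-way result in about 73% to over 99% of trials with a 0.5 SD benefit, assume normal scores, strict selection of the lowest 30% and correlations of 0.4 to 0.8. With 1 SD of selection noise the second range becomes about 44% to 97%.

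This should be corrected. It affects a secondary objective and goes beyond missing detail, since following the plan exactly leaves the hypothesis untested.

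**What to change.** In section 8.4, prespecify for operated infants the within-infant change in AMS and Toronto scores from the last pre-operative exam to the 18- and 30-month visits, with 95% CIs, from a paired analysis or a mixed model. Naming the baseline exam in advance also prevents its being chosen after the data are seen. State whether the 12-month scores listed in section 8.2 are analysed as well.

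Keep the between-group comparison, label it descriptive, and show it beside each group's baseline scores. Do not rely on adjusting it for baseline: where low scores help to define the groups, baseline overlap will be limited and the adjustment would extrapolate.

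The cost is a few sentences of analysis text. Section 4.3.1 already provides for the scores, so no new data are needed. The downside is that change after surgery includes natural recovery, and there is no unoperated comparator of similar severity. The result should be reported as improvement after surgery, not as an effect of surgery.

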9.0 Finance

9.1 Funding

This study is being funded by a grant from Shriners Hospitals for Children. Budgeted funds will be administered by the SHCNC RC and payments to BCH and Gillette Children's Hospital will be approved by [name].

9.2 Costs to Subject

The subject is not anticipated to incur any additional costs at the study center for participation in the study. Costs for the MRI will be covered by grant funds.

10.0 Study Organization

10.1 Multiple PI Plan

The multiple PI plan was chosen because this study includes 3 institutions (Shriners Hospital – Northern California, Boston Children's Hospital, and Gillette Children's Specialty Healthcare), and at each institution, 2 different disciplines (pediatric hand surgeons and pediatric neuroradiologists). The leadership team has worked closely together on the pilot for this study, and 2 of the PIs ([name] & [name]) have successfully collaborated on several research projects. Oversight of the study, along with scientific responsibility, will be provided by [name] and [name]. The neuroradiologists at each institution will be responsible for the MRI studies. [name], [name], and [name] will be responsible for examining the patients and collecting the outcomes data.

10.2 Phone meetings

The PIs will hold conference calls at least quarterly, and the RC at SHCNC will maintain an agenda and minutes for each call. Decisions on scientific direction will be made by the team, after receiving input from all members (representing both specialties and all institutions as appropriate); [name] will make the final decision if any conflicts arise.

Appendix A: MRI Protocol

MRI scanning protocols for brachial plexus consists of the following pulse sequences:

- Each infant will be positioned in an MRI scanner either using a swaddle blanket or vacuum suction controlled infant positioner, the MedVac Immobilizer
- Required sequences:
 - Localizer sequence
 - Sagittal T2 sequence through cervical spine
 - Coronal 3D proton density CUBE (General Electric trade name, Milwaukee, WI) or SPACE (Siemens Medical USA, Malvern, PA) sequence oriented in the plane of the cervical spine and extended anteriorly to include the involved brachial plexus.
 - The total scanning time will be approximately 10-15 minutes excluding initial preparation time. Total study time will be 30 minutes.
- Optional sequences only when time allows and required sequences are diagnostic quality:
 - Coronal T2 fast spine echo
 - Coronal T2 fat saturation CUBE (General Electric trade name, Milwaukee, WI) or SPACE (Siemens Medical USA, Malvern, PA) sequence oriented in the plane of the cervical spine and extended anteriorly to include the involved brachial plexus.
 - Coronal STIR (Short TI Inversion Recovery) CUBE (General Electric trade name, Milwaukee, WI) or SPACE (Siemens Medical USA, Malvern, PA) sequence oriented in the plane of the cervical spine and extended anteriorly to include the involved brachial plexus.
